## 11.2 Figures Shells

Figure PFPConc1

[figure not shown]
Arithmetic Mean (SD) Serum TRL345 Concentration Versus Time Profiles Following Administration of a Single 1-Hour Intravenous Infusion of TRL345 (Linear Scale) (Pharmacokinetic Analysis Population)

Treatments B and C are shifted to the right for ease of reading  
Program: /CAXXXXX/sas\_prg/pksas/adam\_meangraph.sas DDMMMYYY HH:MM  
Program: /CAXXXXX/sas\_prg/pksas/meangraph.sas DDMMMYYY HH:MM

Figure PFPConc2

[figure not shown]
Arithmetic Mean Serum TRL345 Concentration Versus Time Profiles Following Administration of a Single 1-Hour Intravenous Infusion of TRL345 (Linear Scale) (Pharmacokinetic Analysis Population)

Program: /CAXXXXX/sas\_prg/pksas/adam\_meangraph.sas DDMMMYYY HH:MM  
Program: /CAXXXXX/sas\_prg/pksas/meangraph.sas DDMMMYYY HH:MM

Figure PFPConc3

Arithmetic Mean Serum TRL345 Concentration Versus Time Profiles Following Administration of a Single 1-Hour Intravenous Infusion of TRL345 (Semi-log Scale) (Pharmacokinetic Analysis Population)

Program: /CAXXXXXX/sas\_prg/pksas/adam\_meangraph.sas DDMMMYYY HH:MM  
 Program: /CAXXXXXX/sas\_prg/pksas/meangraph.sas DDMMMYYY HH:MM

[figure not shown]
**Notes for Generating the Actual Mean Figures:**

For the arithmetic mean serum TRL345 versus time profiles:

- Legend will be "1 mg/kg TRL345", "10 mg/kg TRL345."
- Y-axis label will be "Serum TRL345 Concentration ( $\mu\text{g/mL}$ )".
- X- axis label will be "Hours From Start of Infusion"
- For figures with SD, add the footnote: "Treatments B is shifted to the right for ease of reading."

## Appendix PFPConc5

Individual Serum TRL345 Concentration Versus Time Profiles Following Administration of a Single 1-Hour Intravenous Infusion of TRL345 (Linear and Semi-log Scale) Subject <#>

Program: /CAXXXXX/sas\_prg/pksas/adam\_indgraph.sas DDMMYYYY HH:MM  
Program: /CAXXXXX/sas\_prg/pksas/indgraph-all.sas DDMMYYYY HH:MM

**Notes for Generating the Actual Individual Figures:**

For the individual serum TRL345 versus time profiles:

- Legend will be "1 mg/kg TRL345", "10 mg/kg TRL345".
- Y-axis label will be "Serum TRL345 Concentration ( $\mu\text{g/mL}$ )".
- X-axis label will be "Hours From Start of Infusion"

### 11.3 Section 14 Summary Tables Shells

Page 1 of X

Table CDS Disposition Summary (Safety Population)

Category	Treatment			Active Total	Overall
	P	A	B		
Dosed	XX (XXX%)	XX (XXX%)	XX (XXX%)	XX (XXX%)	XX (XXX%)
Completed Study	XX ( XX%)	XX ( XX%)	XX ( XX%)	XX ( XX%)	XX ( XX%)
Discontinued From Study	X ( XX%)	X ( XX%)	X ( XX%)	X ( XX%)	X ( XX%)
<Reason>	X ( XX%)	X ( XX%)	X ( XX%)	X ( X%)	X ( X%)

Treatment A: A single 1-hour intravenous infusion of 1 mg/kg TRL345 (Dose Group 1)

Treatment B: A single 1-hour intravenous infusion of 10 mg/kg TRL345 (Dose Group 2)

Treatment P: A single 1-hour intravenous infusion of matching placebo (Dose Groups 1 and 2)

Source: ADaM.ADSL

Program: /CAXXXX/sas\_prg/stsas/tab/programname2022Q1programname2022Q1.sas DDMMYYYY HH:MM

Table CDEM Demographic Summary (Safety Population)

Trait	Category/Statistic	Treatment			Active Total	Overall
		P	A	B		
Sex	Male	X (XX%)	X (XX%)	X (XX%)	X (XX%)	X (XX%)
	Female	X (XX%)	X (XX%)	X (XX%)	X (XX%)	X (XX%)
Race	Asian	X (XX%)	X (XX%)	X (XX%)	X (XX%)	X (XX%)
	Black or African American	X (XX%)	X (XX%)	X (XX%)	X (XX%)	X (XX%)
	White	X (XX%)	X (XX%)	X (XX%)	X (XX%)	X (XX%)
Ethnicity	Hispanic or Latino	X (XX%)	X (XX%)	X (XX%)	X (XX%)	X (XX%)
	Not Hispanic or Latino	X (XX%)	X (XX%)	X (XX%)	X (XX%)	X (XX%)
Age (yr)	n	X	X	X	X	X
	Mean	X.X	X.X	X.X	X.X	X.X
	SD	X.XX	X.XX	X.XX	X.XX	X.XX
	Minimum	XX	XX	XX	XX	XX
	Median	X.X	X.X	X.X	X.X	X.X
	Maximum	XX	XX	XX	XX	XX
	Range	XX	XX	XX	XX	XX
Body Mass Index (kg/m  )	n	X	X	X	X	X
	Mean	X.X	X.X	X.X	X.X	X.X
	SD	X.XX	X.XX	X.XX	X.XX	X.XX
	Minimum	XX	XX	XX	XX	XX
	Median	X.X	X.X	X.X	X.X	X.X
	Maximum	XX	XX	XX	XX	XX
	Range	XX	XX	XX	XX	XX

Treatment A: < >

Treatment B: < >

Treatment P: < >

Descriptive statistics for body mass index, height, and weight are calculated using screening measurements.

Source: ADaM.< >

Program: /CAXXXXX/sas\_prg/stsas/tab/programname2022Q1.sas DDMMYYYY HH:MM

Trellis Bioscience, Inc.  
TRL345, TRL345-102  
Celerion CA34470

Table CPConcl Serum TRL345 Concentrations (µg/mL) Following Administration of a Single 1-Hour Intravenous Infusion of 1 mg/kg TRL345 (Treatment A) (Pharmacokinetic Analysis Population)

Subject Number	Sample Times								
	Day 1					Day 2		Day 3	
	Predose	1	2	4	6	12	24	48	168
X	BLQ	XX	XX	XX	XX	XX	XX	XX	XX
X	BLQ	XX	XX	XX	XX	XX	XX	XX	XX
X	BLQ	XX	XX	XX	XX	XX	XX	XX	XX
n	XX	XX	XX	XX	XX	XX	XX	XX	XX
Mean	XX.X	XX.X	XX.X	XX.X	XX.X	XX.X	XX.X	XX.X	XX.X
SD	XX.XX	XX.XX	XX.XX	XX.XX	XX.XX	XX.XX	XX.XX	XX.XX	XX.XX
CV%	.	XX.X	XX.X	XX.X	XX.X	XX.X	XX.X	XX.X	XX.X
SEM	XX.XX	XX.XX	XX.XX	XX.XX	XX.XX	XX.XX	XX.XX	XX.XX	XX.XX
Minimum	XX	XX	XX	XX	XX	XX	XX	XX	XX
Median	XX.X	XX.X	XX.X	XX.X	XX.X	XX.X	XX.X	XX.X	XX.X
Maximum	XX	XX	XX	XX	XX	XX	XX	XX	XX
Range	XX	XX	XX	XX	XX	XX	XX	XX	XX

For the calculation of summary statistics, values that are below the limit of quantitation (BLQ) of X.XX ug/mL are treated as 0 before the first quantifiable concentration and as missing elsewhere.  
 . = Value missing or not reportable

### Notes for Generating the Actual Table:

#### Presentation of Data:

- Concentrations will be presented to same precision as in bio data.
- The level of precision for each concentrations statistic will be presented as follows: minimum/maximum/range in same precision as in bioanalytical data (i.e., 3 significant figures) and/or concentrations output, mean/median in one more level of precision than minimum/maximum/range, SD/SEM in one more level of precision than mean/median, n will be presented as an integer, and CV%/Geom CV% will be presented to one decimal place.

Programmer Note:

- Wrap concentrations for all days into 1 table with a "Day" column header and "Nominal Time" sub-column header.
- PK time points are as follows:
  - Day 1: Predose (imputed as time 0) and approximately 1 hour  $\pm$  15 minutes (end of infusion [EOI]), 2 hours  $\pm$  15 minutes, 4 hours  $\pm$  15 minutes, 6 hours  $\pm$  15 minutes, and 12 hours  $\pm$  15 minutes post-start of infusion (SOI)
  - Days 2 (24 hours  $\pm$  1 hour post-SOI), 3 (48 hours  $\pm$  1 hour post-SOI), 8 (168 hours post-SOI), 15 (336 hours post-SOI), 29 (672 hours post-SOI), 43 (1008 hours post-SOI), and 76 (1800 hours post-SOI)

Program: /CAXXXX/sas\_prg/pksas/adam\_conc.sas

DDMMYYYY HH:MM

Table CPPar1 Serum TRL345 Pharmacokinetic Parameters Following Administration of a Single 1-Hour Intravenous Infusion of 1 mg/kg TRL345 (Treatment A) (Pharmacokinetic Analysis Population)

Subject Number	Parameters					
	param1 (units)	param2 (units)	param3 (units)	param4 (units)	param5 (units)	param6 (units)
X	XXX	X.XX	XXX	XXX	XX.X	X.XXX
X	XX.X	X.XX	XXX	XXX	XX.X	X.XXX
X	XXX	X.XX	XXX	XXX	XX.X	X.XXX
X	XX.X	X.XX	XXX	XXX	XX.X	X.XXX
X	XX.X	X.XX	XXX	XXX	XX.X	X.XXX
X	X.XX	X.XX	XXX	XXX	XX.X	X.XXX
X	XXX	X.XX	XXX	XXX	XX.X	X.XXX
n	XX	XX	XX	XX	XX	XX
Mean	XXX.X	X.XXX	XXX.X	XXX.X	XX.XX	X.XXXX
SD	XX.XX	XX.XX	XX.XX	XX.XX	XX.XX	XX.XX
CV%	XX.X	XX.X	XX.X	XX.X	XX.X	XX.X
SEM	XX.XX	XX.XX	XX.XX	XX.XX	XX.XX	XX.XX
Minimum	XX.X	X.XX	XXX	XXX	XX.X	X.XXX
Median	XX.XX	X.XXX	XXX.X	XXX.X	XX.XX	X.XXXX
Maximum	XXX	X.XX	XXX	XXX	XX.X	X.XXX
Range	XXX	X.XX	XXX	XXX	XX.X	X.XXX
Geom Mean	XXX.X	X.XXX	XXX.X	XXX.X	XX.XX	X.XXXX
Geom CV%	XX.X	XX.X	XX.X	XX.X	XX.X	XX.X

. = Value missing or not reportable

Program: /CAXXXX/sas\_prg/pksas/pk-tables.sas DDMMYYYY HH:MM

**Notes for Generating the Actual Tables:**

Presentation of Data:

- PK parameters will be presented in the following order and with following units for TRL345 after single 1-hour Intravenous infusion: AUC0-tlast ( $\mu\text{g}\cdot\text{hr}/\text{mL}$ ), AUC0-inf ( $\mu\text{g}\cdot\text{hr}/\text{mL}$ ), AUC%extrap (%), Cmin ( $\mu\text{g}/\text{mL}$ ), Cmax ( $\mu\text{g}/\text{mL}$ ), Ceoi ( $\mu\text{g}/\text{mL}$ ), Tmax (hr), Tmin (hr), Tlast (hr), Kel (1/hr),  $t_{1/2}$  (hr), CL (L/hr), and Vss (L/Kg).
- PK parameters will be reported to 3 significant figures for individual parameters, with the exception of Cmin and Cmax, which will be presented with same level of precision as received from the bioanalytical laboratory, and Tmax, which will be presented with 2 decimal places.
- The level of precision for each parameter statistic will be presented as follows: minimum/maximum/range in same precision as in bioanalytical data (i.e., 3 significant figures) and/or parameter output, mean/median/Geom Mean in one more level of precision than minimum/maximum/range, SD/SEM in one more level of precision than mean/median/Geom Mean, n will be presented as an integer, and CV%/Geom CV% will be presented to one decimal place.

Table ADAD Serum TRL345 ADA Detection Summary Following a Single 1-Hour Intravenous Infusion of TRL345 or Placebo (Immunogenicity Population)

-----Treatment-----				
ADA Result	P (N = X)	A (N = X)	B (N = X)	Active Total (N = X)
-----				
Baseline				
ADA Unevaluable (%)	X (XX%)	X (XX%)	X (XX%)	X (XX%)
ADA Negative (%)	X (XX%)	X (XX%)	X (XX%)	X (XX%)
ADA Positive (%)	X (XX%)	X (XX%)	X (XX%)	X (XX%)
1:X	X (XX%)	X (XX%)	X (XX%)	X (XX%)
1:XX	X (XX%)	X (XX%)	X (XX%)	X (XX%)
1:XXX	X (XX%)	X (XX%)	X (XX%)	X (XX%)
<Days 8, 29 and 43 will be repeated >				
Day 76				
ADA Unevaluable (%)	X (XX%)	X (XX%)	X (XX%)	X (XX%)
ADA Negative (%)	X (XX%)	X (XX%)	X (XX%)	X (XX%)
ADA Positive (%)	X (XX%)	X (XX%)	X (XX%)	X (XX%)
1:X	X (XX%)	X (XX%)	X (XX%)	X (XX%)
1:XX	X (XX%)	X (XX%)	X (XX%)	X (XX%)
1:XXX	X (XX%)	X (XX%)	X (XX%)	X (XX%)
Overall				
ADA Unevaluable (%)	X (XX%)	X (XX%)	X (XX%)	X (XX%)
ADA Negative (%)	X (XX%)	X (XX%)	X (XX%)	X (XX%)
ADA Positive (%)	X (XX%)	X (XX%)	X (XX%)	X (XX%)
-----				

Treatment A: A single 1-hour intravenous infusion of 1 mg/kg TRL345 (Dose Group 1)

Treatment B: A single 1-hour intravenous infusion of 10 mg/kg TRL345 (Dose Group 2)

Treatment P: A single 1-hour intravenous infusion of matching placebo (Dose Groups 1 and 2)

Baseline is the last measurement collected prior to start of dosing.

Overall indicates the number of subjects who had a ADA positive result at one or more time points.

Percentage is relative to the number of subjects (N) dosed.

ADA = Anti-drug antibody; ADA positive = Subject with a confirmed positive ADA result

Program: /CAXXXXX/sas\_prg/stsas/tab\_PROGRAMNAME.sas DDMMYYYY HH:MM

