5.4 Administration of Investigational Product

IV administration of TRL345/placebo will be performed by **blinded**, trained, and qualified site personnel. A calibrated IV infusion pump will be set to deliver the total volume of IP over a 60-minute period. Start and stop times will be recorded in the subject record and eCRF.

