5.7 Management of Infusion Reactions

It is required that all sites have the personnel, equipment, and medications to manage hypersensitivity reactions. Subjects must be monitored closely for signs and symptoms of an infusion reaction (IR) (e.g., fever $>38^{\circ}\text{C}$ (100.4°F), chills, flushing, bradycardia, hyper- or hypotension, itching, flushing urticaria, nausea, vomiting, abdominal pain, chest tightness, angioedema, or respiratory distress). In the event of an IR, the infusion should be slowed or stopped and restarted at the discretion of the Investigator. If a severe IR occurs (Grade 3 or 4 signs or symptoms), discontinue infusion and institute treatment as appropriate. Any infusion-related adverse event will be reported to the SMC within 24 hours.

In addition, if a subject experiences a severe IR, the following procedures will be undertaken:

- A targeted physical examination to capture medically relevant details, including but not limited to, a thorough dermatologic examination; a chest examination for breath sounds, stridor or wheezing; and a cardiac examination with attention to irregular heartbeat.
- Vital signs (sitting or supine blood pressure, heart rate, and body temperature) will be captured at the time of the IR and at least every 15 minutes until the resolution or stabilization of the IR. In addition, hematology and serum chemistry will be taken.

The Investigator may administer any medically indicated pharmacologic agent or procedure intended to relieve symptoms. Signs and symptoms of the IR and drugs given for treatment are to be recorded in the medical record and in the separate electronic case report form (eCRF) page for possible and probable IRs.

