**Table 6–1 Noncompartmental Serum TRL345 Pharmacokinetic Parameters to be Calculated**

Parameter	Label to be Used in the Text, Tables, and Figures*	Definition	Method of Determination
AUC 0-tlast	AUClast	Area under the concentration-time curve from time 0 to the time of the last observed/measured non-zero concentration	Calculated using the Linear Trapezoidal with Linear Interpolation Method
AUC 0-inf	AUC0-inf	Area under the concentration-time curve from time 0 extrapolated to infinity	Calculated as $AUC_{0-inf} = AUC_{0-tlast} + (C_{last}/K_{el})$ where Clast is the last observed/measured concentration
AUC%extrap	AUC%extrap	Percent of AUC0-inf extrapolated	Calculated as $AUC\%extrap = (1 - (AUC_{0-tlast}/AUC_{0-inf})) \times 100$
C coi	Ccoi	Concentration at the end of infusion	Taken directly from bioanalytical data
C min	Cmin	Minimum observed concentration following a single dose corresponding to the single IV dose administration	Taken directly from bioanalytical data
C max	Cmax	Maximum observed concentration	Taken directly from bioanalytical data
T min	Tmin	Time of minimum observed concentration (Cmin) following a single dose corresponding to the single IV dose administration	Taken from clinical database as the difference in the time of administration and the time of the blood draw which is associated with the Cmax
T max	Tmax	Time to reach Cmax; if Cmax occurs at more than 1 time point, Tmax is defined as the first time point with this value	Taken from clinical database as the difference in the time of administration and the time of the blood draw which is associated with the Cmax
T last	Tlast	Time of the last measurable concentration	Taken from clinical database as the difference in the time of administration and the time of the blood draw which is associated with the Clast
λ z	Kel	Apparent first-order terminal elimination rate constant	The negative of the slope of a linear regression of the log(concentration)-time curve for all concentrations > LLOQ
t ½	t½	Apparent first-order terminal elimination half-life	Calculated as $t_{1/2} = 0.693/K_{el}$

Parameter	Label to be Used in the Text, Tables, and Figures*	Definition	Method of Determination
CL	CL	Total serum clearance after IV administration	Calculated as CL = Dose/(AUC0-inf)

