Vss	Vss	Apparent volume of distribution estimated at steady state following a single IV dose administration	Calculated as Vss = MRT0-inf • CL

\*In the text of the CSR, subscripts will be used in parameter names, as appropriate. However, in post-text tables and listings, subscripts will not be used in parameter names.

PK parameters will not be calculated for subjects with less than 3 consecutive postdose time points with quantifiable concentrations. Subjects for whom there are insufficient data to calculate the PK parameters will be included in the concentration tables and individual concentration-time figures and flagged to exclude from the summaries.

For the calculation of the PK parameters, serum concentrations below the limit of quantitation (BLQ) prior to the first quantifiable concentration will be set to 0 and serum concentrations BLQ after the first quantifiable concentration will be treated as missing.

The Kel will be determined using linear regressions composed of at least 3 data points. Furthermore, the Kel will not be assigned if 1) the terminal elimination phase is not apparent, 2) Tmax is one of the last 3 data points, or 3) the R^2 value is less than 0.75. In cases where the Kel interval is not assigned, the values of Kel and Kel-dependent parameters (i.e., AUC0-inf, AUC%extrap, t1/2, CL, and Vss) are considered not calculable and will not be reported. Wherever the resulting t1/2 is more than half as long as the sampling interval, the Kel value and Kel-dependent parameters (i.e., AUC0inf, AUC%extrap, t1/2, CL, and Vss) may not be presented, as judged appropriate and in accordance with Celerion standard operating procedures (SOPs).

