Appendix 16.2.5.3 Test Compound Administration Times (Safety Population)

Dose Group	Subject Number	Study Period	Treatment	Day	Interval	Dose Date	Dose Start Time	Dose End Time	Compound	Planned Dosage	Comments
1	0001	1	A	1	0.00 TO 1.00	DDMONYYYY	HH:MM:SS	HH:MM:SS	TRL345	1 mg/kg	<This column prints only if data is Present>

Treatment A: < >  
 Treatment B: < >  
 Treatment P: < >

Source: SDTM.< >; ADaM. < >  
 Program: /CAXXXX/sas\_prg/stsas/lis/programname2022Q1.sas DDMONYYYY HH:MM

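### The SAP's reporting units for CL (L/hr) and Vss (L/kg) cannot both follow from its own formulas, whichever unit is used for Dose

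*SAP*

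**What the plan says.** SAP Section 2 and Protocol 2.2.2 name CL and Vss among the secondary PK endpoints. SAP Table 6–1 (Section 6.4.1) gives the formulas:

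- Clearance: "Calculated as CL = Dose/(AUC0-inf", closing the bracket after the AUC term.
- Steady-state volume: "Calculated as Vss = MRT0-inf • CL".

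Neither row contains a weight term, and Dose is given no unit or definition. The notes to Table CPPar1 (Section 11.3) set the reporting units: AUC in µg·hr/mL, then "CL (L/hr), and Vss (L/Kg". The notes to Table ITPPar1 (Section 11.1) carry the same pair, so the in-text and post-text tables share the conflict.

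On dose, Protocol 5.3 sets the amount from Day 1 weight, so the mg given differ between subjects within a dose group. SAP Section 6.4.1 calls for actual sample times in the PK calculations but does not mention actual dose. The administration listing shell (SAP Appendix 16.2.5.3) has a column headed "Planned Dosage", filled with 1 mg/kg as its example, and none for mg or mL infused. Protocol 5.7 provides that after an infusion reaction "the infusion should be slowed or stopped and restarted at the discretion of the Investigator".

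**The concern.** Multiplying a clearance by a time cannot introduce a per-kg term. If CL is in L/hr, Vss from the Table 6–1 formula is in litres. If Vss is in L/kg, the CL behind it is in L/hr/kg. A programmer who follows both the formula table and the table notes must attach a wrong unit to one of them.

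The mismatch equals each subject's own weight, and both parameters are named endpoints of a first-in-human study. Protocol 1.3.2 reports the rat Vss per kg (305 mL/kg), so human Vss per kg is the figure that a reader would set beside it. The missing step also leaves a choice open: the dose is set on Day 1 weight, but SAP Section 8.3 summarises Screening weight, so whoever adds a division by weight has to guess which to use.

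A second and separate gap is that Dose could be read as planned or as infused. That produces no body-weight factor, but it would bias CL and Vss for any subject whose infused amount differed from plan.

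**Working it through.** **Inputs.** CL = Dose/AUC0-inf and Vss = MRT0-inf × CL (SAP Table 6–1). AUC is in µg·hr/mL, which equals mg·hr/L (notes to Table CPPar1). MRT is in hr. The documents state no human CL or Vss, so the figure to reproduce is the printed pair of units.

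**Unit check**

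| Dose basis | CL = Dose/AUC | Printed L/hr? | Vss = MRT × CL | Printed L/kg? |
|---|---|---|---|---|
| mg | mg ÷ (mg·hr/L) = L/hr | yes | hr × L/hr = L | no |
| mg/kg | (mg/kg) ÷ (mg·hr/L) = L/hr/kg | no | hr × L/hr/kg = L/kg | yes |

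Neither row reproduces the printed pair.

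**Size.** For a given subject the two bases differ by mg ÷ (mg/kg) = body weight in kg. The documents give BMI limits but no weights. Over assumed weights of 50, 70 and 120 kg the factor is 50, 70 and 120, at either dose level.

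**Illustration at 70 kg.** Assume an AUC0-inf of 5000 µg·hr/mL per mg/kg and an MRT of 400 hr. These values are only illustrative, and the ratio does not depend on them. At 1 mg/kg:

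- mg basis: CL = 70/5000 = 0.014 L/hr; Vss = 400 × 0.014 = 5.6 L.
- mg/kg basis: CL = 1/5000 = 0.0002 L/hr/kg; Vss = 400 × 0.0002 = 0.08 L/kg.
- Ratio: 0.014/0.0002 = 70 and 5.6/0.08 = 70.

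At 10 mg/kg dose and AUC both rise tenfold under the same assumption, and the results are identical.

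On the mg basis, 5.6 would be printed under L/kg where 0.08 is meant. Against the rat value of 0.305 L/kg it would read as 5.6/0.305 ≈ 18 times higher, when the correct comparison is 0.08/0.305 ≈ 0.26. On the mg/kg basis, 0.0002 would be printed under L/hr where 0.014 is meant.

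**Planned versus infused dose.** AUC reflects what was infused, so CL computed on planned dose is true CL × planned/infused. Vss inherits the same ratio through CL.

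| Fraction infused | Multiplier on CL and Vss |
|---|---|
| 80% | 1/0.8 = 1.25 |
| 120% | 1/1.2 = 0.83 |
| 50% | 1/0.5 = 2.0 |

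**The case against.** The best defence is that nothing has yet been calculated wrongly. The units stand in programming notes, SAP Section 11 says the shells may change, and an analyst who enters Dose in mg and then divides Vss by weight gets exactly the printed pair. A gross error would also probably be noticed: 5.6 L/kg at 70 kg implies 5.6 × 70 = 392 L. This is fair and limits the point to a specification error. It does not remove it, because the division is written nowhere, the weight to use is not named, and no other text reconciles the formulas with the labels.

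On dose, the defence is stronger. SAP Section 4 sends dosing errors and incomplete data to the pharmacokineticist for case-by-case review and possible exclusion from the PK Analysis Population, so a half-delivered infusion would probably be caught. An infusion that is slowed, or stopped and restarted, may still deliver the full amount. What remains is that the review can exclude a subject but does not say which dose enters the calculation for a subject who is kept.

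A reader might be tempted to go further in three ways that the documents do not support:

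- That the eCRF holds only infusion times. Protocol 5.4 says "Start and stop times will be recorded in the subject record and eCRF", which does not exclude other fields. The eCRF and the Pharmacy Manual are not in the documents, and Protocol 5.6 requires records of the amount dispensed to each subject.
- That dose errors up to 20% go unreported. The threshold in Protocol 9.10 defines one kind of important deviation. Sites also report under their IRB rules, and SAP Section 8.2 has the site's deviations carried into the CSR.
- That the comparison between dose groups is blurred. Each parameter carries one unit in both groups, and the planned comparison across groups uses AUC and half-life, which the conflict does not touch.

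**Conclusion.** The unit conflict is real and can be established from the SAP alone. If the formulas and labels are both followed as written, either Vss is overstated or CL is understated by a factor equal to body weight: about 70-fold at an assumed 70 kg, and 50- to 120-fold over assumed weights of 50 to 120 kg. The documents do not show which of the two is affected. It would be too strong to say that an endpoint is already wrong, since a corrected label or an added division avoids the error.

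The undefined Dose is a lesser, separate gap. Its effect is planned/infused, for example 1.25-fold at 80% delivered, and it arises only if planned dose is used and the infused amount differs from it.

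Cmax, Cmin, AUC and half-life are unaffected. Table 6–1 also has no row for MRT0-inf, but whether half the infusion time is subtracted hardly matters: 0.5 hr against the assumed 400 hr is about 0.1%.

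**What to change.** In SAP Table 6–1 and in the notes to Tables ITPPar1 and CPPar1, do one of the following:

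- put both parameters on one basis, either CL in L/hr with Vss in L, or CL in L/hr/kg with Vss in L/kg; or
- keep the printed units and add the step Vss (L/kg) = MRT0-inf × CL / body weight, naming Day 1 weight, which sets the dose.

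Any consistent choice will do. If a per-kg basis is chosen, name Day 1 weight there too.

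In the same edit, state in Section 6.4.1 that Dose is the amount actually infused, in mg, to match the existing rule on actual sample times.

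The cost is a few lines of SAP text and the matching programming. It changes no trial procedure. The sponsor should confirm that the infused amount can be obtained from the dosing records, since the documents do not show the eCRF.
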